8.2 Continued Treatment beyond Progression of Disease

Accumulating evidence indicates a minority of patients treated with immunotherapy may derive clinical benefit from continued treatment despite initial evidence of progressive disease [48]. For this reason, patients receiving nivolumab +/- [ipilimumab] will be permitted to continue study therapy beyond initial investigator-assessed RECIST 1.1-defined progression as long as they meet the 2 criteria listed below.

- Investigator-assessed clinical benefit, and
- Subject is tolerating study drug

The assessment of clinical benefit should take into account whether the subject is clinically deteriorating and unlikely to receive further benefit from continued treatment. All decisions to continue treatment beyond initial progression post-surgery must be discussed with the MDACC IND Office and documented in the study records.

Patients should discontinue study therapy upon evidence of further progression, defined as an additional 10% or greater increase in tumor burden from time of initial progression (including all target lesions and new measurable lesions).

New lesions are considered measurable at the time of initial progression if the longest diameter is at least 10 mm (except for pathological lymph nodes, which must have a short axis of at least 15 mm). Any new lesion considered non-measurable at the time of initial progression may become measurable and therefore included in the tumor burden measurement if the longest diameter increases to at least 10 mm (except for pathological lymph nodes, which must have an increase in short axis to at least 15 mm).

For statistical analyses that include the investigator-assessed progression date, patients who continue treatment beyond initial investigator-assessed, RECIST 1.1-defined progression will be considered to have investigator-assessed progressive disease at the time of the initial progression event.

8.3 Destruction of Study Drug

Nivolumab and ipilimumab are to be destroyed onsite. It is the Investigator's responsibility to ensure that arrangements have been made for disposal and that procedures for proper disposal have been established according to applicable regulations, guidelines, and institutional procedures. Appropriate records of the disposal must be maintained.

8.4 Return of Study Drug

If study drug will not be destroyed upon completion or termination of the study, all unused and/or partially used study drug that was supplied by BMS must be returned to BMS. The return of study drug will be arranged by BMS. It is the investigator's responsibility to arrange for disposal of all empty containers, provided that procedures for proper disposal have been established according to applicable federal, state, local, and institutional guidelines and procedures, and provided that appropriate records of disposal are kept.

9.0 CONCOMITANT THERAPY

Concurrent medications related to co-morbidity (e.g. hypertension, diabetes, etc.) and pre-medications prescribed by the protocol for infusion reactions will be recorded in the database. Hydration, supportive medications, and routine surgical drugs will not be recorded in the database. The patient will provide a list of medications taken within 4 weeks prior to screening, and will provide a new list during each clinic visit (see section 10.0). The name, dose, date of start, date of stop (if use for short term), indication of the medication will be listed.

The patient should not start a new prescription medication or over-the-counter medication before consulting with the study investigator, except in the case of a medical emergency. No other cancer/investigational therapies should be started during the current study without consulting with the study investigator.

10.0 STUDY ASSESSMENTS AND PROCEDURES

Table 1: Study Assessments and Procedures for Arm A

Trial Period:	Screening Phase	Treatment Cycles. 3 cycles (2-Week Cycles) planned before surgery then after surgery (4-Week Cycles), patients may receive up to 2 years of therapy depending on response and every restaging scans every 12 weeks							End of Treatment	Post-treatment		
					Surgery					Discontinue	Safety Follow-up ¹	Follow-Up Visits
Title:	Screening											
Treatment Cycle/Day:	0	C1D1	C2D1	C3D1	C4D1	C5D1	C6D1	C7+D1	At time of discon	30 days post last dose	Every 9 weeks post-discon	Every 12 weeks
Scheduling Window (Days) ^b	-28 to -1	±3	±3	±3	±7	±3	±3	±3	±3	±7	±7	±7
Administrative Procedures												
Informed consent	X											
Informed consent for future biomedical research (optional)	X											
Inclusion/exclusion criteria	X											

Trial Period:	Screening Phase	Treatment Cycles. 3 cycles (2-Week Cycles) planned before surgery then after surgery (4-Week Cycles), patients may receive up to 2 years of therapy depending on response and every restaging scans every 12 weeks							End of Treatment	Post-treatment		
Title:	Screening				Surgery				Discontinue	Safety Follow-up¹	Follow-Up Visits	Survival Follow-Up^a
Treatment Cycle/Day:	0	C1D1	C2D1	C3D1	C4D1	C5D1	C6D1	C7+D1	At time of discon	30 days post last dose	Every 9 weeks post-discon	Every 12 weeks
Scheduling Window (Days)^b	-28 to -1	±3	±3	±3	±7	±3	±3	±3	±3	±7	±7	±7
Demographics and medical history	X											
Prior and concomitant medication review	X	X	X	X	X	X	X	X	X	X		
Post-study anticancer therapy status										X	X	X
Survival status												X
Clinical Procedures/Assessments												
Review adverse events	X	X	X	X	X	X	X	X	X	X	X	
Full physical examination	X								X	X		
Directed physical examination ^c		X	X	X	X	X	X	X				
Child-Pugh score	X											
Height, weight, and vital signs (T, P, RR, BP) ^c	X	X	X	X	X	X	X	X	X			
12-Lead electrocardiogram	X											
Upper endoscopy ^p	X											
ECOG performance status	X ^e	X	X	X	X	X	X	X	X			
Nivolumab administration		X ^b	X	X		X ^b	X	X				
LOCAL Laboratory Assessments												
Pregnancy test ^d	X	X				X				X		
PT/INR and PTT	X ^e	X	X	X	X	X	X	X	X	X		
CBC with differential ^f	X ^e	X	X	X	X	X	X	X	X	X		

Trial Period:	Screening Phase	Treatment Cycles. 3 cycles (2-Week Cycles) planned before surgery then after surgery (4-Week Cycles), patients may receive up to 2 years of therapy depending on response and every restaging scans every 12 weeks							End of Treatment	Post-treatment		
Title:	Screening				Surgery				Discontinue	Safety Follow-up¹	Follow-Up Visits	Survival Follow-Up^a
Treatment Cycle/Day:	0	C1D1	C2D1	C3D1	C4D1	C5D1	C6D1	C7+D1	At time of discon	30 days post last dose	Every 9 weeks post-discon	Every 12 weeks
Scheduling Window (Days)^b	-28 to -1	±3	±3	±3	±7	±3	±3	±3	±3	±7	±7	±7
Chemistry panel ^f	X ^e	X	X	X	X	X	X	X	X	X		
Urinalysis ^g	X ^e	X	X	X	X		X ^q		X			
T3, FT4, TSH, ACTH, and total cortisol ^g	X ^e	X	X	X	X		X ^q		X	X		
AFP ^p	X ^e	X			X		X ^q		X	X		
C -Reactive protein, amylase, lipase		X			X		X ^q		X			
Serum IGF	X ^q	X			X		X ^q		X			
Hepatitis C antibody (HCV Ab, anti-HCV)	X											
Anti-HBc (Total and IgM), anti-HBs, HBsAg	X											
If Anti-HCV (Hepatitis C antibody) positive:												
• HCV genotype	X											
• HCV viral load ⁿ	X	X			X		X ^q		X			
If (1) HBsAg positive or (2) anti-HBc positive, anti-HBs negative, and HBsAg negative:												
• Anti-HDV	X											
• Anti-HBe and HBeAg	X											

Trial Period:	Screening Phase	Treatment Cycles. 3 cycles (2-Week Cycles) planned before surgery then after surgery (4-Week Cycles), patients may receive up to 2 years of therapy depending on response and every restaging scans every 12 weeks							End of Treatment	Post-treatment		
					Surgery					Discontinue	Safety Follow-up ^l	Follow-Up Visits
Title:	Screening											
Treatment Cycle/Day:	0	C1D1	C2D1	C3D1	C4D1	C5D1	C6D1	C7+D1	At time of discon	30 days post last dose	Every 9 weeks post-discon	Every 12 weeks
Scheduling Window (Days) ^b	-28 to -1	±3	±3	±3	±7	±3	±3	±3	±3	±7	±7	±7
• HBV viral load ⁿ	X				X		X ^q		X			
• Anti-HBc (total), anti-HBs, and HBe Ag	X											
CENTRAL Laboratory Assessments												
Blood for genetic analysis		X										
Whole blood for biomarker studies (serum and plasma) ^h		X	X	X	X		X ^q		X			
Whole blood for correlative studies (RNA and DNA) ^h		X	X	X	X		X ^q		X			
Tumor tissue collection ^j	X				X							
Efficacy Measurements												
Tumor imaging ^k	X ^{i, n}				X		X ^q		X			

AFP = alpha fetoprotein; aPTT = activated partial thromboplastin time; Anti-HBc (total) = Total hepatitis B core antibody; Anti-HDV = hepatitis D virus antibody (previously known as 'delta'); anti-HBs = hepatitis B surface antibody; BP = blood pressure; CBC = complete blood count; Discon = discontinuation; ECOG = Eastern Cooperative Oncology Group; FT4 = free thyroxine; HBeAb or anti-HBe = hepatitis B e antibody; HBeAg = hepatitis B e antigen; HBV = hepatitis B virus; HBcAg = hepatitis B core antigen; HBsAb = hepatitis B surface antibody; HBsAg = hepatitis B surface antigen; HCV = hepatitis C virus; HCV Ab = hepatitis C antibody; INR = international normalized ratio; P = pulse; Q12W = every 12 weeks; RR = respiratory rate; T = temperature; PT = prothrombin time; T3 = triiodothyronine; TSH = thyroid-stimulating hormone, ACTH = adrenocorticotropic hormone .

- a. In subjects that experience site-assessed PD or start a new anti-cancer therapy, contact should be made (example; by telephone) q12W to assess for survival status.
- b. Cycle 1 treatment must be given within 3 days of allocation. The window for each visit is ± 3 days until the end of treatment and ± 7 days during follow-up. Nivolumab is given every 4 weeks after surgery.
- c. Height will be measured at Visit 1 only.
- d. For women of reproductive potential, a urine or serum pregnancy test should be performed within 24 hours prior to C1D1, C5D1 and 30 days post treatment. May use screening pregnancy test if performed within 24 hours of first dose. A serum test can be done if urine is not appropriate. Additionally, if urine test is positive or is not evaluable, a serum test is required. Subjects must be excluded/discontinued in the event of a positive test results. Pregnancy tests (serum and/or urine tests) should be repeated if required by local guidelines.
- e. ECOG Performance Status and laboratory tests for screening and determining eligibility are to be performed within 28 days prior to the first dose of trial treatment.
- f. CBC with differential and chemistry to be performed every 2 weeks before surgery. After surgery, CBC with differential and chemistry are performed on every nivolumab administration day.
- g. Urinalysis and thyroid/hormonal function tests will be performed at every cycle before surgery, at time of surgery (C4D1), at C6D1 and at every restaging thereafter (q12 weeks).
- h. Blood will be collected prior to dose one (C1D1), Cycle 2 and 3 (before the 2nd and 3rd dose of Nivolumab), at time of surgery (C4D1), at 8 weeks after surgery (C6D1), at every restaging thereafter (q12 weeks), and finally at treatment discontinuation (confirmed progression or end of therapy).
- i. Screening tumor imaging will be performed within 28 days prior to allocation for confirmation of baseline measurable disease per RECIST 1.1 as required prior to subject allocation, then at time of surgery. After surgery, imaging will be repeated and therapy starts at C7D1, then surveillance imaging will be repeated q12W (72 \pm 7 days).
- j. Biopsies will be required pre-treatment and at time of surgery.
- k. The first on-study imaging time point will be performed at 6 weeks around time of surgery (42 \pm 7 days) calculated from the date of allocation and then 8 weeks after surgery, and will continue to be performed q12W.
- l. SAEs will be followed through 100 days following cessation of treatment, or 100 days following cessation of treatment if the subject initiates new anticancer therapy, whichever is earlier.
- m. HBV/HCV viral loads (for subjects who have known history of chronic infection) will be measured during screening, then at C1D1, at time of surgery (C4D1), at 8 weeks after surgery (C6D1), at every restaging thereafter (q12 weeks), and at time of discontinuation.
- n. The following imaging studies are required at screening, at time of surgery, at 8 weeks after surgery, then at every restaging thereafter (q12 weeks): CT chest with or without contrast; MRI of abdomen and pelvis with or without contrast unless patient has contraindication for MRI or severely claustrophobic.
- o. Every time imaging is done for re-staging (q12 weeks).

Trial Period:	Screening Phase	Treatment Cycles. 3 cycles (2-Week Cycles) planned before surgery then after surgery (4-Week Cycles), patients may receive up to 2 years of therapy depending on response and every restaging scans every 12 weeks							End of Treatment	Post-treatment		
Title:	Screening				Surgery				Discontinue	Safety Follow-up ^l	Follow-Up Visits	Survival Follow-Up ^a
Treatment Cycle/Day:	0	C1D1	C2D1	C3D1	C4D1	C5D1	C6D1	C7+D1	At time of discon	30 days post last dose	Every 9 weeks post-discon	Every 12 weeks
Scheduling Window (Days) ^b	-28 to -1	±3	±3	±3	±7	±3	±3	±3	±3	±7	±7	±7

p. Unless performed within 6 months of enrollment day.
 
q. Starting with Cycle 6, assessments are to be done q12 weeks.
												

Table 1: Study Assessments and Procedures for Arm B

Trial Period:	Screening Phase	Treatment Cycles. 3 cycles (2-Week Cycles) planned before surgery then after surgery (4-Week Cycles), patients may receive up to 2 years of therapy depending on response and every restaging scans every 12 weeks							End of Treatment	Post-treatment		
Title:	Screening				Surgery				Discontinue	Safety Follow-up ^m	Follow-Up Visits	Survival Follow-Up ^a
Treatment Cycle/Day	0	C1D1	C2D1	C3D1	C4D1	C5D1	C6D1	C7+D1	At time of discon	30 days post last dose	Every 9 weeks post-discon	Every 12 weeks
Scheduling Window (Days) ^b	-28 to -1	±3	±3	±3	±7	±3	±3	±3	±3	±7	±7	±7
Administrative Procedures												
Informed consent	X											
Informed consent for future biomedical research (optional)	X											
Inclusion/exclusion criteria	X											
Demographics and medical history	X											
Prior and concomitant medication review	X	X	X	X	X	X	X	X	X	X		

Post-study anticancer therapy status										X	X	X
Survival status												X
Clinical Procedures/Assessments												
Review adverse events	X	X	X	X	X	X	X	X	X	X	X	
Full physical examination	X								X	X		
Directed physical examination ^c		X	X	X	X	X	X	X				
Child-Pugh score	X											
Height, weight, and vital signs (T, P, RR, BP) ^c	X	X	X	X	X	X	X	X	X			
12-Lead electrocardiogram	X											
Upper endoscopy	X											
ECOG performance status	X ^e	X	X	X	X	X	X	X	X			
Nivolumab administration		X ^b	X	X		X ^b	X	X				
Ipilimumab administration		X ^b				X ^f						
LOCAL Laboratory Assessments												
Pregnancy test ^d	X	X				X				X		
PT/INR and PTT	X ^e	X	X	X	X	X	X	X	X	X		
CBC with differential ^f	X ^e	X	X	X	X	X	X	X	X	X		
Chemistry panel ^f	X ^e	X	X	X	X	X	X	X	X	X		
Urinalysis ^g	X ^e	X	X	X	X		X ^q		X			
T3, FT4, TSH, ACTH, and total cortisol ^g	X ^e	X	X	X	X		X ^q		X	X		
AFP ^o	X ^e	X			X		X ^q		X	X		
C -Reactive protein, amylase, lipase		X			X		X ^q		X			
Serum IGF	X ^q	X			X		X ^q		X			
Hepatitis C antibody (HCV Ab, anti-HCV)	X											
Anti-HBc (Total and IgM), anti-HBs, HBsAg	X											
If Anti-HCV (Hepatitis C antibody) positive:												
• HCV genotype	X											
• HCV viral load ⁿ	X	X			X		X ^q		X			

If (1) HBsAg positive or (2) anti-HBc positive, anti-HBs negative, and HBsAg negative:												
• Anti-HDV	X											
• Anti-HBe and HBeAg	X											
• HBV viral load ^m	X				X		X ^q		X			
• Anti-HBc (total), anti-HBs, and HBe Ag	X											
CENTRAL Laboratory Assessments												
Blood for genetic analysis		X										
Whole blood for biomarker studies (serum and plasma) ^h		X	X	X	X		X ^q		X			
Whole blood for correlative studies (RNA and DNA) ^h		X	X	X	X		X ^q		X			
Tumor tissue collection ^j	X				X							
Efficacy Measurements												
Tumor imaging ^k	X ^{i,n}				X		X ^q		X			

AFP = alpha fetoprotein; aPTT = activated partial thromboplastin time; Anti-HBc (total) = Total hepatitis B core antibody; Anti-HDV = hepatitis D virus antibody (previously known as 'delta'); anti-HBs = hepatitis B surface antibody; BP = blood pressure; CBC = complete blood count; Discon = discontinuation; ECOG = Eastern Cooperative Oncology Group; FT4 = free thyroxine; HBeAb or anti-HBe = hepatitis B e antibody; HBeAg = hepatitis B e antigen; HBV = hepatitis B virus; HBcAg = hepatitis B core antigen; HBsAb = hepatitis B surface antibody; HBsAg = hepatitis B surface antigen; HCV = hepatitis C virus; HCV Ab = hepatitis C antibody; INR = international normalized ratio; P = pulse; Q12W = every 12 weeks; RR = respiratory rate; T = temperature; PT = prothrombin time; T3 = triiodothyronine; TSH = thyroid-stimulating hormone, ACTH = adrenocorticotrophic hormone .

- a. In subjects that experience site-assessed PD or start a new anti-cancer therapy, contact should be made (example; by telephone) q12W to assess for survival status.
- b. Cycle 1 treatment must be given within 3 days of allocation. The window for each visit is ±3 days until the end of treatment and ±7 days during follow-up. Nivolumab is given every 4 weeks after surgery.
- c. Height will be measured at Visit 1 only. Timepoints of directed physical examination will follow nivolumab and ipilimumab administration day.
- d. For women of reproductive potential, a urine or serum pregnancy test should be performed within 24 hours prior to C1D1, C5D1 and 30 days post treatment. May use screening pregnancy test if performed within 24 hours of first dose. A serum test can be done if urine is not appropriate. Additionally, if urine test is positive or is not evaluable, a serum test is required. Subjects must be excluded/discontinued in the event of a positive test results. Pregnancy tests (serum and/or urine tests) should be repeated if required by local guidelines.
- e. ECOG Performance Status and laboratory tests for screening and determining eligibility are to be performed within 28 days prior to the first dose of trial treatment.
- f. CBC with differential and chemistry to be performed every 2 weeks before surgery. After surgery, CBC with differential and chemistry are performed on every nivolumab and ipilimumab's administration day.

- g. Urinalysis and thyroid/hormonal function tests will be performed at every cycle before surgery, at time of surgery (C4D1), at C6D1 and at every restaging thereafter (q12 weeks).
- h. Blood will be collected prior to dose one (C1D1), Cycle 2 and 3 (before the 2nd and 3rd dose of Nivolumab), at time of surgery (C4D1), at 8 weeks after surgery (C6D1), at every restaging thereafter (q12 weeks), and finally at treatment discontinuation (confirmed progression or end of therapy).
- i. Screening tumor imaging will be performed within 28 days prior to allocation for confirmation of baseline measurable disease per RECIST 1.1 as required prior to subject allocation, then at time of surgery. After surgery, imaging will be repeated and therapy starts at C7D1, then surveillance imaging will be repeated q12W (72±7 days).
- j. Biopsies will be required pre-treatment and at time of surgery.
- k. The first on-study imaging time point will be performed at 8 weeks around time of surgery (42±7 days) calculated from the date of allocation and then 8 weeks after surgery, and will continue to be performed q12W.
- l. SAEs will be followed through 100 days following cessation of treatment, or 100 days following cessation of treatment if the subject initiates new anticancer therapy, whichever is earlier.
- m. HBV/HCV viral loads (for subjects who have known history of chronic infection) will be measured during screening, then at C1D1, at time of surgery (C4D1), at 8 weeks after surgery (C6D1), at every restaging thereafter (q12 weeks), and at time of discontinuation.
- n. The following imaging studies are required at screening, at time of surgery, at 8 weeks after surgery, then at every restaging thereafter (q12 weeks): CT chest with or without contrast; MRI of abdomen and pelvis with or without contrast unless patient has contraindication for MRI or severely claustrophobic.
- o. Every time imaging is done for re-staging (q12 weeks).
- p. Unless performed within 6 months of enrollment day.
- q. Starting with Cycle 6, assessments are to be done q12 weeks.
- r. Ipilimumab 1 mg/kg IV is administered in the adjuvant setting, starting with Cycle 5, every 6 weeks to 4 doses maximum.

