After finishing the last treatment, hepatic resection or biopsy will occur on day 1 of week 7 (+/- 7 days). We will obtain surveillance scans (MRI of abdomen and pelvis with/without contrast, and CT chest with/without contrast of chest) 8 weeks after surgery. Patients who show significant progression of disease post-operatively will be taken off study and an optional biopsy will be taken at that time for immunological analysis.

Patients who complete the study or discontinue study treatment should be scheduled for an end of treatment visit (EOT) as soon as possible. All patients who complete the study or discontinue treatment will have a safety follow-up visit 30 (+/- 14 days) after the last dose of study drug or surgery, whichever comes last. Please refer to **Figure 2** below for the study design.

Patients will receive baseline staging studies with CT or MRI and be assessed for treatment response by scans: MRI or CT of abdomen and pelvis with/without contrast, and CT chest with/without contrast of chest (according to RECIST 1.1 and irRC) at week 6 (+/- 7 days). Each patient will have post-surgical (day 1 of week 11 +/- 7 days), staging studies as above. Subsequently, restaging will be carried out every 12 weeks unless, in the investigators' opinion, follow-up intervals need to be shorter. Studies to confirm a complete response or document progressive disease will be performed as needed. Patients will be allowed to continue study therapy after initial investigator-assessed RECIST 1.1/irRC-defined progression if they are deemed by the investigator to be deriving clinical benefit and tolerating study drug(s), as described in Section 8.3.

[figure not shown]

Figure 2. Study Design of preoperative nivolumab alone or in combination with ipilimumab. There are 2 arms to this study: A) Nivolumab monotherapy in resectable HCC; B) Combination nivolumab plus ipilimumab in resectable HCC.

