10.1.3 Pre-surgical Visit

During the Pre-Surgical Evaluation, the patient will have labs and imaging performed and be assessed by the physician and surgeon to determine if they are still good candidates for surgery. For the pre-surgical visit, patients will return to the clinic at week 6 (+/- 7 days). The following assessments will be conducted during this visit:

- Vital Signs Measurement
- Physical examination
- ECOG Performance Status
- Blood samples for Immune Tests
- Hematology, PT and PTT
- Serum chemistry (see Section 10)
- Amylase and Lipase
- AFP
- T3 (free), T4 (free) & TSH (see Section 10)
- ACTH and Total Cortisol
- Concomitant medications (see Section 9)
- Adverse event assessment
- Each patient will be restaged with CT of the chest, abdomen and pelvis or MRI abdomen/pelvis at baseline, prior to surgery, 8 weeks post-surgery follow up, and during future follow up visits (every 12 weeks) as indicated in Section 10, unless, in the investigators' opinion, follow-up intervals need to be shorter. Studies to confirm a complete response or document progressive disease will be performed as needed.

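### Table 1 gives 12-weekly surveillance imaging as 72±7 days instead of 84±7 (both arms), and Arm B footnote k labels the 42-day scan as 8 weeks

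*Combined protocol and SAP*

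**What the plan says.** Section 10.0 has one schedule table per arm, both numbered Table 1.

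- **Footnote i, Arm B:** "then surveillance imaging will be repeated q12W (72±7 days". Arm A footnote i also says "then surveillance imaging will be repeated q12W", followed by the same 72±7 days.
- **Abbreviation list under the tables:** "Q12W = every 12 weeks".
- **Section 5.3:** "Subsequently, restaging will be carried out every 12 weeks", unless the investigators judge that shorter intervals are needed. Sections 10.1.2, 10.1.3 and 10.1.5 also give 12 weeks.
- **Footnote k, Arm B:** "The first on-study imaging time point will be performed at 8 weeks around time of surgery (42±7 days", counted from allocation.
- **Footnote k, Arm A:** "The first on-study imaging time point will be performed at 6 weeks around time of surgery", with the same 42±7 days.
- **Section 5.3, all patients:** response is assessed by scan "according to RECIST 1.1 and irRC) at week 6 (+/- 7 days". Section 10.1.3 says of the pre-surgical visit, which includes imaging, that "patients will return to the clinic at week 6 (+/- 7 days".

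**The concern.** Footnote i is where the 12-week interval is turned into a number of days with a tolerance, and that number is wrong. Section 10.1 points to Table 1 for the frequency and timing of measurements, so a coordinator or monitor could reasonably work from it. A scan done exactly at 12 weeks would then be logged as out of window. Alternatively, scans would be booked at 72 days and drift ahead of the intended calendar. Scan dates decide when progression is recorded for TTP and PFS (Sections 12.2.2.2 and 12.2.2.3). Footnotes g, h and m tie hormone tests, research bloods and viral loads to the same restaging visits.

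The Arm B footnote k error is of a different kind: the week label contradicts the day count in the same sentence. Taken alone, the label would put the presurgical response scan after the planned operation.

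**Working it through.** **Footnote i (both arms).** Inputs are an interval of 12 weeks (abbreviation list and Section 5.3) and a printed value of 72±7 days.

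- 12 × 7 = 84 days. The printed 72 is not reproduced: 72 / 7 = 10.3, which is not a whole number of weeks.
- Printed window: 72 − 7 = 65 to 72 + 7 = 79. Day 84 lies 84 − 79 = 5 days beyond it.
- Correct window: 84 − 7 = 77 to 84 + 7 = 91. The two windows share only days 77 to 79.
- Three 4-week nivolumab cycles are 3 × 28 = 84 days, so the 12-week interval also fits the dosing calendar. An interval of 72 days does not.

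**Effect if 72 days were followed.** I assume surgery on day 1 of week 7 (6 × 7 + 1 = day 43) and follow-up to two years from first cycle (day 730). The protocol is not consistent on when 12-weekly surveillance starts, so three starting points are shown.

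| Surveillance counted from | Days left | ÷ 72 | ÷ 84 | Completed scans |
|---|---|---|---|---|
| 8 weeks after surgery: 43 + 56 = day 99 | 730 − 99 = 631 | 8.8 | 7.5 | 8 v 7 |
| Day 1 of week 11: 10 × 7 + 1 = day 71 | 730 − 71 = 659 | 9.2 | 7.8 | 9 v 7 |
| C7D1, two 4-week cycles after C5D1 on day 71: 71 + 56 = day 127 | 730 − 127 = 603 | 8.4 | 7.2 | 8 v 7 |

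Each round comes 84 − 72 = 12 days early, so after seven rounds the calendar is 7 × 12 = 84 days ahead, one full intended interval. If progression is uniform within an interval, mean detection lag is half the interval: 72 / 2 = 36 days against 84 / 2 = 42. The difference of 6 days is smaller than the ±7-day tolerance.

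**Footnote k (Arm B).** Inputs are the 8-week label and 42±7 days from allocation.

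- 8 × 7 = 56 days. The printed window is 42 − 7 = 35 to 42 + 7 = 49, and 56 lies outside it.
- 42 / 7 = 6 weeks exactly, which agrees with Arm A footnote k and Section 5.3. The day count is right and the week label is wrong.
- Counting from first dose does not rescue the label. Cycle 1 must start within 3 days of allocation, and surgery on day 43 is 42 days after first dose, ±7. The latest on-schedule surgery is therefore 3 + 42 + 7 = 52 days after allocation, still before day 56.

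The 8 weeks after surgery mentioned later in footnote k is a different time point and is not in error.

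**The case against.** The case for leaving this alone is that it is clerical. In footnote i the 12-week code stands directly before the wrong parenthesis, and Section 5.3, the visit sections and several other footnotes all say 12 weeks. Section 10.1 describes Table 1 as a summary and sends the reader on to those sections for detail. Section 5.3 allows shorter intervals at the investigators' discretion, so a 72-day scan is not forbidden in any case. Section 12.6 gives PFS only a Kaplan-Meier estimate per arm. Footnote k carries its own correct day count. Its two versions differ by one digit, so a misread character in the text cannot be wholly excluded there. Enrollment had stopped by January 8, 2020, so few if any first scans would remain to be scheduled.

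Most of this stands, and it is why the point is minor. It does not make 72 right. The discretion to scan earlier excuses a 72-day scan but does nothing for an 84-day scan, which is the scheduled one and falls outside the stated window. Footnote i carries the same figure in both tables, so a stray misread is an unlikely explanation for it. Treatment can run for two years from first cycle, so the window still matters for ongoing surveillance and for judging deviations in data already collected.

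**Conclusion.** Both errors hold, at minor severity. Footnote i is wrong as written in both arms: 72±7 days should be 84±7. Footnote k in Arm B has the wrong week label beside a correct day count, and that part is close to editorial.

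Following footnote i literally would add one surveillance scan over two years, or two if counting starts at week 11. It would advance the mean dating of progression by about 6 days. These figures rest on surgery on day 43, follow-up to day 730 and uniform progression within intervals. The footnote i error is common to both arms and so does not bias their comparison. It does not set the presurgical response scan, and no sample size, confidence interval or decision rule depends on it.

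**What to change.** Change 72±7 days to 84±7 days in footnote i of both tables. Change 8 weeks to 6 weeks in Arm B footnote k, after a glance at the source PDF to confirm the digit. That is three footnote figures, with no change to design or analysis.

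The correction does not settle when surveillance begins. Section 5.3 puts the first post-surgical scan both at 8 weeks after surgery and at day 1 of week 11, and footnote i refers to C7D1 where footnotes h, k and n point to 8 weeks after surgery. That needs its own decision and could be made in the same amendment.
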